Amendment 1	19 September 2017	
All changes were made prior to start of the study and made per FDA comments except where indicated. Other minor changes were added for clarity.
 
Schedule of Activities for the Intensive and Non-intensive Studies and applied throughout protocol:
 
• For bone marrow assessments, bone marrow aspirates are required; however, we now added preference for bone marrow biopsies in addition to aspirates. In the event of an inadequate aspirate, a bone marrow biopsy is required.• Baseline genetics edits made for clarification that known genetics at the time of randomization will be used to stratify participants.• Red blood cell and platelet transfusion history required 8 and not 24 weeks prior to randomization for the nonintensive study only.• Added windows for follow-up assessments. 
Schedule of Activities for the Intensive Study only:

Document History		
Document	Version Date	Summary and Rationale for Changes
		
• Removed collection of prior transfusions; only collect during study.• Changed from every 28 day to weekly chemistries.• Consolidation with cytarabine changed from 13 g/m^2 to 3 g/m^2 for adults <60 years and 1 g/m^2 for adults ≥ 60 years.• Following HSCT, participants will not be allowed to have \geqGrade 2 GVHD before resuming glasdegib/placebo. 
PGIC not collected at baseline for non-intensive study, updated as a correction
 
Table 2: Made a correction by adding the time, 1 hour post-dose, for the column labeled “Glasdegib following chemotherapy”.
 
Cycle ≥ 1, Day 1
 
Secondary Endpoint (Section 2 and throughout protocol): added CR with partial hematologic recovery (CRh) for the Non-intensive study only.
 
CCI [REDACTED]
 
Inclusion Criterion 5: removed one single dose of Ara-C of up to 2 grams for control of blasts counts.
 
Exclusion Criterion 10: clarified that dose equivalent of $\geq 550 \text{ mg/m}^2$ of daunorubicin is a criterion for the Intensive Chemotherapy study only.
 
Dose Modifications (Section 5.5.5): clarified glasdegib or placebo does not be delayed or dose reduced for Grade 3/Grade 4 nonhematologic, study treatment related toxicity and should be permanently discontinued if interruptions are for more than 28 consecutive days.
 
Concurrent administration of herbal preparations prohibited (Section 5.8.1), added as a clarification since it is already an exclusion criterion.

Document History		
Document	Version Date	Summary and Rationale for Changes
		
Prophylactic Intrathecal Chemotherapy allowed per investigator discretion in Permitted Concomitant Medications in Section 5.8.2.
 
Efficacy Assessments (Section 7.2) now includes definition for CR with partial hematologic recovery for the Non-intensive study.
 
Immunophenotyping and Genetics (Section 7.2.2) clarifications added regarding requirement to stratify based on known genetic risk classification at the time of randomization.
 
Section 9.3.2: Added updated definitions for EFS and includes CR/CRh as response (in duration of response and time to response endpoints) for the nonintensive study. Added additional sensitivity analyses for EFS.
 
Appendix 4: Added response definition for CRh and clarified CRI requires either criteria for residual neutropenia or thrombocytopenia must be met.
 
Appendix 14: added ELN Risk Stratification by Genetics table.
 
General spelling and grammar issues corrected.
 
CCI
 
Original protocol	27 July 2017	N/A

10.14. Appendix 14: Letters Sent to Investigators After Amendment 5

The following letters were sent to investigators after Amendment 5, but the content of the letters are no longer relevant in this amendment:

[Letter dated 12 Jun 2019](#)

[Letter dated 09 Apr 2020](#)

10.15. Appendix 15: Abbreviations

The following is a list of abbreviations that may be used in the protocol.

Abbreviation	Term
AE	adverse event
AIDS	acquired immunodeficiency syndrome
ALT	alanine aminotransferase
AML	acute myeloid leukemia
APL	acute promyelocytic leukemia
aPTT	activated partial thromboplastin time
Ara-C	cytarabine
AST	aspartate aminotransferase
ATRA	all-trans retinoic acid
AUC	area under the plasma concentration curve
AUC _{inf}	area under the plasma concentration-time profile from time 0 to infinity
AV	atrioventricular
BM	bone marrow
BST	Best Supportive Therapy
BUN	blood urea nitrogen
Ca	calcium
CFR	Code of Federal Regulations
CI	confidence interval
CIOMS	Council for International Organizations of Medical Sciences
CK	creatinine kinase
C _{max}	maximum plasma concentration
CMM _L	chronic myelomonocytic leukemia
COVID-19	Coronavirus Disease 2019
CPK	creatine phosphokinase
CR	complete remission
CRF	case report form
CRh	complete remission with partial hematologic recovery
CRi	complete remission with incomplete hematologic recovery
CR _{MRD-neg}	complete remission with negative minimal residual disease
CRO	contract research organization
CSF	cerebrospinal fluid
CSR	clinical study report
CT	Clinical Trial
CTCAE	Common Terminology Criteria for Adverse Events
C _{trough}	plasma trough concentration
CYP	cytochrome P450
DILI	drug-induced liver injury
DNA	deoxyribonucleic acid
DU	dispensable units

Abbreviation	Term
EC	Ethics Committee
ECG	electrocardiogram
ECOG	Eastern Cooperative Oncology Group
eCRF	electronic Case Report Form
EDP	Exposure During Pregnancy
EDMC	External Data Monitoring Committee
EFS	event-free survival
ELN	European Leukemia Net
EMA	European Medicines Agency
EMD	Extra Medulary Disease
EU	European Union
EudraCT	European Clinical Trials Database
FDA	Food and Drug Administration (United States)
FLT3-ITD	fms-like tyrosine kinase internal tandem duplication
FSH	follicle-stimulating hormone
GCP	Good Clinical Practice
G-CSF	granulocyte colony-stimulating factor
GGT	gamma-glutamyl transferase
GM-CSF	granulocyte macrophage colony-stimulating factor
GnRH	gonadotropin-releasing hormone
GVHD	graft-versus-host disease
HDPE	high-density polyethylene
HIPAA	Health Insurance Portability and Accountability Act
HGRAC	Human Genetics Resources Administration of China
Hh	Hedgehog
HI	hematologic improvement
HIV	human immunodeficiency virus
HR	heart rate
HRT	hormone replacement therapy
HSCT	hematopoietic stem cell transplant
IB	Investigator's Brochure
ICD	informed consent document
ICH	International Conference on Harmonization
IEC	Independent Ethics Committee
IMP	investigational medicinal product
IND	investigational new drug application
INR	international normalized ratio
INT	intensive
IP	investigational product
IPAL	Investigational Product Accountability Log
IRB	Institutional Review Board
IRT	interactive response technology
IWR	Interactive Web Response

Abbreviation	Term
IV	intravenous
IVR	Interactive Voice Response
K	potassium
LDAC	low dose cytarabine
LDH	lactate dehydrogenase
LFT	liver function test
LIC	lead-in cohort
LS	least squares
LSLV	last subject last visit
MDS	myelodysplastic syndrome
MedDRA	Medical Dictionary for Regulatory Activities
Mg	magnesium
mQTcF	mean QTcF
MRD	minimal residual disease
NA	not applicable
Na	sodium
NCI	National Cancer Institute
NIH	National Institutes of Health
NIMP	non-investigational medicinal product
NINT	non-intensive
NNRTI	non-nucleoside reverse transcriptase inhibitors
OS	overall survival
PD	pharmacodynamics
PGIC	Patient Global Impression of Change
PGIS	Patient Global Impression of Symptoms
PK	Pharmacokinetics
PRO	patient reported outcomes
PT	prothrombin time
PTT	partial thromboplastin time
PVC	premature ventricular contraction/complex
Q	quartile
QD	once a day
QTc	corrected QT
QTcF	corrected QT (Fridericia method)
RBC	red blood cell
RNA	ribonucleic acid
SAE	serious adverse event
SAP	statistical analysis plan
SARS-CoV2	severe acute respiratory syndrome coronavirus 2
SC	Subcutaneous
SD	standard deviation
SoA	schedule of activities
SOP	standard operating procedure

Abbreviation	Term
SPC	Summary of Product Characteristics
SRSD	single reference safety document
SSRI	selective serotonin reuptake inhibitor
SUSAR	suspected unexpected serious adverse reactions
TBili	total bilirubin
TdP	Torsade de Pointes
TEAE	treatment emergent adverse event
TOC	Table of Contents
U/A	urinalysis
ULN	upper limit of normal
US	United States
USPI	United States Prescribing Information
UTI	urinary tract infection
UVB	ultraviolet B light
UV	University of Washington
Vit	vitamin
WBC	white blood cell
WHO	World Health Organization
WOCBP	woman of childbearing potential

11. REFERENCES (Not Applicable)

## 1. VERSION HISTORY

This Statistical Analysis Plan (SAP) for study B1371019 is based on Protocol Amendment #6 dated 02 Feb2021.

**Table 1. Summary of Major Changes in SAP Amendments**

SAP Version	Change	Rationale
1	Not Applicable	Not Applicable
2	The PRO sections were revised following comments from FDA. Minor clarifications were made in other sections.	Following Protocol Amendment #2
3	The Pharmacogenomics Analysis Set was removed.  Clarification regarding select endpoints were made (CRI or better, and CRh or better).  Add analysis method for China subset patients.	Following Protocol Amendment #3 and satisfying CFDA requirement
4	Region (rest of world versus China) added as a stratification factor to the applicable efficacy analyses for the intensive study.  Updated the definition of “on-treatment” for assessments and treatment-emergent adverse events.	Following Protocol Amendment #5
5	Add OS subgroup analysis.  Add sensitivity analyses for handling potential missing or unclean data due to COVID-19.	Following FDA feedback
6	SAP is updated throughout.	Following Protocol Amendment #6

	
The efficacy analysis is no longer applicable.
 
The safety analysis will be conducted for B1371019 and B1371012 separately and independently.
	
--	--	--

## 2. INTRODUCTION

This SAP provides the detailed methodology for summary and statistical analyses of the safety data collected in study B1371019 Protocol Amendment 6. This analysis plan is meant to supplement the study protocol. Any deviations from this analysis plan will be described in the Clinical Study Report.

The purpose of Protocol Amendment 6 is to provide continued access to study intervention (azacitidine with or without glasdegib), and collection of safety data for eligible participants who continue to derive a clinical benefit from study treatment in studies B1371019 and B1371012. The safety analyses of participants from Study B1371019 and participants originating from Parent Study B1371012 will be conducted separately and independently. The safety analysis set will include all participants who receive at least one dose of study treatment after consenting to Protocol Amendment 6.

### 2.1. Study Objective

Type	Objectives	Endpoints	Additional Definitions	Analyses and Summaries
Safety	To monitor the safety and tolerability of the investigational drugs in participants continuing study intervention from this study and participants originating from Parent Study B1371012.	All AEs and SAEs	Section 3.3	Section 6.3.1

### 2.2. Study Design

Study design is as described in the B1371019 Protocol (Amendment 5, 12 April 2019) and Study B1371012 Protocol (Amendment 7, 14 June 2018). This is an open-label, continuation protocol for eligible NINT cohort participants enrolled in Study B1371019 or Study B1371012 eligible participants.

A maximum of 34 participants from Study B1371019 and 3 participants from Study B1371012 may continue to access to study intervention.

### **3. ENDPOINTS AND BASELINE VARIABLES: DEFINITIONS AND CONVENTIONS**

#### **3.1. Efficacy Endpoint**

Not Applicable.

#### **3.2. Baseline Variables**

The date of first dose (start date) of study treatment is the earliest date of non-zero dosing of any study drug. The date of last dose of study treatment is the latest date of non-zero dosing of any study drug.

No windowing will be applied when defining baseline. Any deviations from the protocol specified window will be documented as protocol deviations.

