6.1.2. Dosing Regimen

- Azacitidine will be administered 75 mg/m²/day for 7 days every 28 days on Days 1-7 (± 3 days) per local label or per the IP Manual (or SPC). Azacitidine may be administered by SC injection or IV infusion. Alternate dosing schedules to administer the 7 doses to accommodate participant and treatment center availability are allowed. The starting dose regimen will be the same as the most recent regimen received on the B1371019 or B1371012 study.
- Glasdegib 50, 75 or 100 mg will be orally administered daily and continuously. The starting dose regimen will be the same as the most recent regimen received on the B1371012 or B1371019 study.

Dose modifications are discussed in [Section 6.6](#).

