9.4.1. Safety Endpoint(s)

All participants who receive any study treatment (safety analysis set) will be included in the summaries and listings of safety data. Overall safety profile and tolerability of azacitidine or glasdegib + azacitidine will be characterized by type, frequency, severity, seriousness, timing, and relationship to study therapy of AEs.

AEs will be classified using the MedDRA classification system. The severity of the toxicities will be graded according to the NCI CTCAE version 4.03.

In all summaries, emphasis will be placed on TEAEs (events occurring from Amendment 6 consent up to last dose + 28 days). AEs will be summarized by the frequency of participants experiencing TEAEs corresponding to body systems and MedDRA preferred term and by worst NCI CTCAE (version 4.03) grade.

AEs leading to permanent discontinuation of any study treatment, and SAEs will be considered with special attention. AE reporting, including SUSARs, will be carried out in accordance with applicable local regulations. Reasons for discontinuation from study treatment will be summarized by the frequency of participants with each reason described.

Descriptive statistics ie, number of non-missing values and number of missing values (ie, n [missing]), mean, median, SD, minimum, maximum and first and third quartile (Q1 and Q3) for treatment duration ([last dose date - first dose date after Amendment 6 consent +1]/7) will be provided.

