#### **6.2.3.1. Exposure to Glasdegib**

The summary of treatment exposure for glasdegib will include the following information:

- Treatment duration (weeks).

The duration of glasdegib (in weeks) is defined as:

$$\text{Treatment duration (weeks)} = (\text{last dose date} - \text{first dose date} + 1)/7.$$

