### **6.2.3.5. Exposure to Azacitidine (Non-intensive Study Only)**

The summary of treatment exposure for azacitidine will include the following information:

- Treatment duration (weeks).

Azacitidine is administered by subcutaneous injection (SC) or intravenous (IV) infusion 75 mg/m^2 daily for 7 days, in 28 day cycles.

The dose level for azacitidine captured in the CRF is calculated as actual dose administered/body surface area (BSA) (mg/m^2). The last available weight of the patient on or prior to the day of dosing will be used.

The duration of azacitidine (in weeks) during the study for a patient is defined as:

$$\text{Treatment duration (weeks)} = (\text{last dose date} - \text{first dose date} + 1)/7.$$

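### The SAP's treatment-duration formula omits the protocol's Amendment 6 starting point, so read literally it can count earlier exposure

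*SAP*

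**What the plan says.** Protocol 9.4.1 promises descriptive statistics for "treatment duration ([last dose date - first dose date after Amendment 6 consent +1]/7) will be provided". The clock starts at the first dose that follows consent to Amendment 6.

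The SAP gives the duration separately for each drug. In 6.2.3.1, "The duration of glasdegib (in weeks) is defined as" last dose date minus first dose date plus one, divided by seven. In 6.2.3.5, "The duration of azacitidine (in weeks) during the study for a patient is defined as" the same expression. Neither mentions Amendment 6 consent. The only definition of first dose that these formulas can draw on is in SAP 3.2: "The date of first dose (start date) of study treatment is the earliest date of non-zero dosing of any study drug". SAP 5.2.2 sets the start day for study day in the same unrestricted way, and SAP 3.3 starts the on-treatment period at the first non-zero dose, again with no mention of Amendment 6.

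The SAP does state the restriction in other places. On the analysis set, SAP 2 says: "The safety analysis set will include all participants who receive at least one dose of study treatment after consenting to Protocol Amendment 6". SAP 4 repeats this, and SAP 6 counts treatment-emergent events from Amendment 6 consent.

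**The concern.** In a trial where treatment begins after enrolment, leaving out the anchor would do no harm, because the earliest dose and the first dose on protocol are the same. Here they are not. Inclusion criterion 1 admits people who are benefiting from ongoing study treatment, and Protocol 6.1.2 carries their dosing forward: "The starting dose regimen will be the same as the most recent regimen received on the B1371012 or B1371019 study". Each of them has a dosing history before the Amendment 6 consent date, so the choice of first dose determines the result.

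Two things are at stake. The first is that the report may not contain the exposure measure that the protocol specifies. SAP 2 requires the study report to describe departures from the SAP, so a programmer who follows the SAP to the letter would have nothing to declare. The second is context: safety is the only objective of this amendment, and duration on each drug is the background against which adverse event frequencies are read.

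**Working it through.** The documents state no exposure figure for Amendment 6, so there is none to reproduce. The check compares definitions and then does date arithmetic.

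**Definitions**

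| Item | Protocol 9.4.1 | SAP |
|---|---|---|
| Start of duration | First dose after Amendment 6 consent | Earliest non-zero dose (3.2, used by 6.2.3.1 and 6.2.3.5) |
| Unit | Treatment, not split by drug | Formula per drug, but 3.2 defines first dose across any drug |
| Start of adverse event window | Amendment 6 consent | Amendment 6 consent (6), or first non-zero dose (3.3 and 3.3.1, to which 6.3.1 refers) |

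**Excess.** Let A be weeks of treatment under Amendment 6 and P be weeks from the earlier first dose to the first dose after consent. The protocol gives A. The SAP read literally gives A + P. The excess is P, whatever the last dose date.

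**Bound on P for B1371019.** The amendment history (Protocol Appendix 13) says that the Amendment 3 changes, dated 01 March 2018, were made before the study started. Amendment 6 is dated 02 February 2021. The interval is 1,069 days; 1,069 / 7 = 152.7 weeks, and 1,069 / 365.25 = 2.93 years. The document date stands in for the consent date, so the bound is slightly longer for anyone who consented later. For B1371012 the documents give no start date and P cannot be bounded.

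**Illustration.** No first-dose dates and no Amendment 6 treatment lengths are given, so both A and P below are assumptions, apart from the last row, where P is the bound. Cells show A + P in weeks, with (A + P)/A in brackets.

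| P | A = 12 | A = 26 | A = 52 |
|---|---|---|---|
| 26 | 38 (3.2) | 52 (2.0) | 78 (1.5) |
| 52 | 64 (5.3) | 78 (3.0) | 104 (2.0) |
| 104 | 116 (9.7) | 130 (5.0) | 156 (3.0) |
| 152.7 | 164.7 (13.7) | 178.7 (6.9) | 204.7 (3.9) |

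**How this meets the adverse event tables.**

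- If events are counted as in SAP 6 and exposure as in SAP 3.2, Amendment 6 events appear beside a longer exposure period.
- If events follow the unanchored period in SAP 3.3, events and exposure may cover the same time, but both depart from Protocol 9.4.1.
- Only if both are anchored to Amendment 6 does the report match the protocol.

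**The case against.** The strongest reply is that the SAP needs no anchor because its scope supplies one. SAP 2 confines the plan to "statistical analyses of the safety data collected in study B1371019 Protocol Amendment 6" and calls it a supplement to the protocol. A supplement that is silent can be read together with the protocol's explicit formula. This has some force: the SAP leaves a condition out, and nowhere says that doses before Amendment 6 count. But a general scope sentence does not redefine first dose, and the SAP writes the condition out for the analysis set and the Section 6 event window while omitting it here. The SAP also keeps terms that do not fit an open-label continuation, such as blinded therapy (6.2.2.1) and a long-term follow-up phase (5.3.1). That makes it plausible, though not shown, that 3.2 was carried over from the earlier design.

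A reader might infer more than the documents support:

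- **That the sponsor chose to measure lifetime exposure.** The text is an omission, open to a narrower reading.
- **That continued treatment will look safer per unit of time.** The mismatch arises only if events follow SAP 6, whereas SAP 6.3.1 points to the definition in 3.3.1. Events are reported as participant frequencies, and no exposure-adjusted rate is planned.
- **That the two source studies would be compared on different clocks.** The SAP does not say whether doses given under B1371012 count, but the two groups are analysed separately and independently, so no planned result sets one duration against the other.
- **That exposure will be inflated 6.9-fold or more.** Ratios of that size in the last row divide an outer bound by an assumed treatment length; they are not estimates.

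**Conclusion.** Wrong as written; should be fixed. Followed literally in participants already on treatment, the SAP does not produce the duration defined in Protocol 9.4.1. The excess equals each participant's earlier treatment time. For B1371019 that is at most about 153 weeks, given that nobody started before 01 March 2018 and taking the amendment date for consent. The actual size cannot be found from the documents. The consequence is limited to descriptive reporting in at most 34 participants from B1371019 and 3 from B1371012. The conclusion rests on reading SAP 3.2 as the definition behind the formulas in 6.2.3; on the narrower reading of SAP scope the numbers would be right, but the text would still need to say so.

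**What to change.** 1. In SAP 6.2.3.1 and 6.2.3.5, define duration in weeks as (last dose date of that drug − first non-zero dose date of that drug after Amendment 6 consent + 1)/7. This restores the protocol's anchor and removes the clash between a formula per drug and a first dose defined across drugs.
2. Add the same Amendment 6 condition to the first-dose definition in SAP 3.2 and the start day in 5.2.2.
3. Align the on-treatment period in SAP 3.3 with the window in Protocol 9.4.1 and SAP 6, which opens at Amendment 6 consent. This needs its own edit: anchoring first dose alone would still leave out events between consent and the next dose.
4. Total exposure since the original start of treatment is optional. If shown, it should be a separate, labelled line, limited to participants whose dates are available.

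The cost is SAP wording and one derivation. The Schedule of Activities (Protocol 1.3) already puts the Amendment 6 consent date and dosing information on the CRF. The reported exposure will be shorter than under the literal reading.

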##### **3.2.1. Stratification**

Not applicable.

#### **3.3. Safety Endpoints**

Safety endpoints will be summarized based on the on-treatment period unless otherwise specified.

On-treatment is defined as the time from the first non-zero dose of study treatment to the last non-zero dose + 28 days.

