8.3.1. Time Period and Frequency for Collecting AE and SAE Information

The time period for actively eliciting and collecting AEs and SAEs (“active collection period”) for each participant begins from the time the participant provides informed consent, which is obtained before the participant’s participation in the study (ie, before undergoing any study-related procedure and/or receiving study intervention), through and including a minimum of 28 calendar days after the last administration of the study intervention.

Follow-up by the investigator continues throughout and after the active collection period and until the AE or SAE or its sequelae resolve or stabilize at a level acceptable to the investigator and Pfizer concurs with that assessment.

For participants who are screen failures, the active collection period ends when screen failure status is determined.

If the participant withdraws from the study and also withdraws consent for the collection of future information, the active collection period ends when consent is withdrawn.

If a participant definitively discontinues or temporarily discontinues study intervention because of an AE or SAE, the AE or SAE must be recorded on the CRF and the SAE reported using the CT SAE Report Form.

Investigators are not obligated to actively seek AEs or SAEs after the participant has concluded study participation. However, if the investigator learns of any SAE, including a death, at any time after a participant has completed the study, and he/she considers the event to be reasonably related to the study intervention, the investigator must promptly report the SAE to Pfizer using the CT SAE Report Form.

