##### **3.3.1. Adverse Events**

An adverse event is considered treatment emergent (TEAE) relative to a given treatment if the event occurs during the on-treatment period (regardless if it was seen prior to the start of treatment). An adverse event is considered treatment-related as assigned by the investigator.

Adverse events (AEs) will be coded to preferred term (PT) and system organ class (SOC) using the Medical Dictionary for Regulatory Activities (MedDRA) and classified by severity using the National Cancer Institutes (NCI) Common Terminology Criteria for Adverse Events (CTCAE), version 4.03. Adverse events occurring on the same day as the first dose of study treatment will be considered to have occurred during the on-treatment period. All other assessments which occur on the same day as the first dose of study treatment will be considered as baseline assessments.

Safety data collected outside the on-treatment period as described above will be listed but not summarized.

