### **5.3.1. Missing Dates**

For purposes of data listings, dates will reflect only the information provided by the investigator on the CRF.

If start dates for adverse events are completely missing a worst case approach will be taken whereby the events will be considered treatment emergent. If only partial information are available (eg, only a month and year or only a year) and the partial information provide sufficient information to indicate the dates are prior to the start of study treatment (eg, month/year less than month/year of first dose) then these will be considered to have started prior to treatment; otherwise a similar worst case approach will apply and these will be considered to have started after treatment.

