### **AE Onset Date:**

The following imputation rules apply if the event is unique for a patient or it is the first of a series of similar events; otherwise, the AE Onset Date will not be imputed:

- If the AE Collection Date is not missing, is less than the Date of First Exposure to Treatment, and is less than the AE Stop Date, then AE Onset Date is set to the Date of AE Collection.
- If the Previous Visit Date is greater than the Date of First Exposure to Treatment and less than the AE Stop Date, the AE Start Date is set to the previous visit date.

- If the Date of First Exposure to Treatment is greater than the previous visit date and less than the AE Stop Date, the AE Onset Date is set to the Date of First Exposure to Treatment.
- Otherwise AE Onset Date is set to the AE Stop Date.

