## **6. ANALYSES AND SUMMARIES**

Analyses for B1371019 and B1371012 will be conducted separately and independently.

All participants who receive any study treatment (safety analysis set) will be included in the summaries and listings of safety data. Overall safety profile and tolerability of azacitidine or glasdegib + azacitidine will be characterized by type, frequency, severity, seriousness, timing, and relationship to study therapy of AEs.

AEs will be classified using the MedDRA classification system. The severity of the toxicities will be graded according to the NCI CTCAE version 4.03.

In all summaries, emphasis will be placed on TEAEs (events occurring from Amendment 6 consent up to last dose + 28 days). AEs will be summarized by the frequency of participants experiencing TEAEs corresponding to body systems and MedDRA preferred term and by worst NCI CTCAE (version 4.03) grade.

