### **6.3.1. Adverse Events**

All analyses will be based on treatment emergent events unless otherwise specified. Treatment emergent is defined in [Section 3.3.1](#).

Seriousness, toxicity grade, study drug action taken (interruption, reduction, and withdraw) are as reported by the investigator on the adverse event CRF.

Summaries by treatment arm, SOC and PT in decreasing frequency based on the frequencies observed in the glasdegib arm will be provided for:

- Treatment Emergent Events by Maximum Toxicity Grade (All Causality);
- Treatment Emergent Events by Maximum Toxicity Grade (Treatment Related); Serious Treatment Emergent Events by Maximum Toxicity Grade (All Causality);
- Serious Treatment Emergent Events by Maximum Toxicity Grade (Treatment Related).

An event will be considered treatment related if the investigator considered the event related to the study drug or this information is unknown.

- Treatment Emergent Adverse Events Leading to Dose Interruptions by Maximum Toxicity Grade (All Causality) separately for each study drug, for chemotherapy, and for any study treatment;
- Treatment Emergent Adverse Events Leading to Dose Reductions by Maximum Toxicity Grade (All Causality) separately for each study drug, for chemotherapy, and for any study treatment;
- Treatment Emergent Adverse Events Leading to Permanent Withdrawal by Maximum Toxicity Grade (All Causality) separately for each study drug, for chemotherapy, and for any study treatment;
- Serious Treatment Emergent Events (All Causality).

Each patient will be counted only once within each PT.

As described in [Section 5.3.2](#), in case a patient has events with missing and non-missing toxicity grades, the maximum of the non-missing grade will be displayed. Missing grade will only be displayed in the event that only one event has been reported for a patient and the grade is missing.

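### The SAP gives two start points, first non-zero dose and Amendment 6 consent, for the treatment-emergent window of its only endpoint

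*SAP*

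**What the plan says.** SAP 3.3 sets the period on which safety endpoints are summarized: "On-treatment is defined as the time from the first non-zero dose of study treatment to the last non-zero dose + 28 days". SAP 3.3.1 makes an AE treatment emergent if it falls in that period, and adds: "Safety data collected outside the on-treatment period as described above will be listed but not summarized". SAP 6.3.1, which lists the AE tables, says "All analyses will be based on treatment emergent events unless otherwise specified" and refers back to SAP 3.3.1 for the meaning.

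SAP 6, the parent section of those tables, says that in every summary "emphasis will be placed on TEAEs (events occurring from Amendment 6 consent up to last dose + 28 days". Protocol 9.4.1 uses the same words.

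AE collection under Protocol 8.3.1 "begins from the time the participant provides informed consent", so events before the first dose are on the CRF. SAP 3.2 takes first dose as the earliest date on which any study drug was given at a non-zero dose and does not mention Amendment 6. SAP 5.3.1 classes a partly dated AE as pre-treatment when the available information shows that "the dates are prior to the start of study treatment (eg, month/year less than month/year of first dose").

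**The concern.** Both rules close 28 days after the last dose. Only the start differs, and no passage says which start prevails. Every planned TEAE table, including those for public disclosure in SAP 6.3.1.1, depends on this date. Two programmers working from the same SAP could produce different counts from the same data, and each could cite a section in support.

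The interval between consent and first dose is foreseen by the design. The Schedule of Activities in Protocol 1.3 has a Screening column separate from Day 1, with re-consent and AE monitoring marked in both.

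**Working it through.** The plan states no figure on this point, so there is none to reproduce. The check compares the texts and then sizes the difference from the dosing schedule.

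**1. The two rules**

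- Rule A (SAP 3.3, 3.3.1, 6.3.1): first non-zero dose to last non-zero dose + 28 days. Anything outside is listed only.
- Rule B (SAP 6, Protocol 9.4.1): Amendment 6 consent to last dose + 28 days.

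**2. What first dose means under Rule A**

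- *Reading (i), first dose after Amendment 6 consent.* This fits the analysis set in SAP 2, and Protocol 9.4.1 uses it for treatment duration. Rule A then opens on or after the consent date. An AE between consent and that dose is a TEAE under B and listed only under A.
- *Reading (ii), SAP 3.2 taken literally.* These participants were already on treatment in B1371019 or B1371012, so the earliest non-zero dose precedes Amendment 6. Rule A then admits earlier events that B excludes.

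The rules agree only when consent and the first dose used fall on the same day.

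**3. Length of the gap under reading (i)**

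Inputs: azacitidine on Days 1-7 of a 28-day cycle and glasdegib daily without a break (Protocol 6.1.2); a Day 1 visit window of -3/+14 days (Protocol 1.3). Assumption: consent on a dosing day precedes that day's dose.

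- Consent at a Day 1 dosing visit: 0 days.
- Uninterrupted daily glasdegib: about 0 to 1 day.
- Azacitidine alone, uninterrupted cycle, next dose on Day 29: gap = 29 - consent day. Day 8 gives 21 days, Day 15 gives 14, Day 22 gives 7 and Day 28 gives 1. Days 1-7 give 0.
- Azacitidine alone, consent on Day 8, next visit at the end of its window: 21 + 14 = 35 days. It is longer still if the cycle is extended for toxicity (Protocol 6.1.1).

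The gap can therefore differ between the arms of B1371019.

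**4. Consequence for the disclosure table**

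SAP 6.3.1.1 reports non-serious TEAEs, by preferred term, that occur in more than 5% of either arm. Arm sizes are not given; B1371019 has at most 34 participants in total (SAP 2.2). Suppose the choice of rule adds one participant to the count for a term:

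- Arm of 19 or fewer: 0 to 1 participant crosses the threshold (1/19 = 5.3%). If both arms are represented, the smaller has at most 17 (1/17 = 5.9%).
- Arm of 20 to 34: one participant alone does not cross (1/20 = 5.0%, which is not above 5%). A term already counted in one participant does cross when a second is added (2/34 = 5.9%).
- B1371012, at most 3 participants: with all three, 1/3 = 33.3%.

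The added participant must have no event with the same preferred term in the Rule A window, because SAP 6.3.1 counts each patient once per term.

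**5. Partial dates under reading (i)**

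Assumed dates: consent on 12 March (Day 8), next azacitidine dose on 2 April (21 days later), AE onset recorded only as March. SAP 5.3.1 compares March with April and classes the event as pre-treatment. Compared with the consent month, March is not earlier than March, so the worst-case approach in the same section makes it treatment emergent.

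**The case against.** The strongest reply is that SAP 3.3 and 6.3.1 both give way where something else is specified, and SAP 6, which speaks of all summaries, could be that specification. The reply is weakened because SAP 6.3.1, the more specific section, points back to SAP 3.3.1. Each rule can claim priority.

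Second, SAP 5.3 hands partial dates and the treatment-emergent algorithm to a CDISC Safety Rulebook that the documents do not reproduce. It may settle the matter in practice. It does not do so on the page, and the SAP does not say that it overrides either definition.

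Third, the effect is small: there is no hypothesis, the tables are descriptive, and events outside the window are still listed. This stands and limits the weight of the point.

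Two stronger readings are tempting and should not be drawn:

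- *That the class of an AE with no onset date depends on when it was recorded.* The onset rules in SAP 5.3.1 can suggest this. For an event collected before first exposure and before its stop date, "then AE Onset Date is set to the Date of AE Collection". For one still ongoing at first exposure, with the previous visit earlier, "the AE Onset Date is set to the Date of First Exposure to Treatment". But the opening of SAP 5.3.1 treats AEs with completely missing start dates as treatment emergent in every case. At most the two parts of that section pull against each other.
- *That a stated share of the observation window is lost.* Any such percentage needs an assumed consent day, an assumed number of cycles and reading (i). It would count calendar days, not AEs. Under reading (ii) nothing after consent is lost.

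**Conclusion.** The inconsistency is real and should be resolved before the tables are programmed. It rests on the wording alone and needs no assumption about missing data.

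The direction depends on what first dose means. Under reading (i), Rule A leaves out of the tables events that the protocol's definition counts. Under reading (ii), it brings in events that the protocol's definition excludes. The day counts apply to reading (i) only. The 21-day figure also assumes azacitidine alone, dosing on exactly Days 1-7, consent on Day 8 and no delay.

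The documents do not allow an estimate of how many AEs are affected, and for many participants the answer may be none. No inferential conclusion is at risk. What can change is the tabulated counts and, at these sample sizes, whether a preferred term appears in the disclosure table.

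**What to change.** 1. In SAP 3.3.1, define a TEAE as an AE with onset on or after the Amendment 6 consent date and no later than 28 days after the last dose, matching SAP 6 and Protocol 9.4.1. Exempt these events from the sentence that restricts out-of-period data to listings. Leave the on-treatment period and the baseline-assessment sentence anchored at first dose for other data; moving the on-treatment period itself to consent would clash with the rule that assessments on the first-dose day are baseline. The cross-reference in SAP 6.3.1 can then stay as it is.
2. In SAP 5.3.1, compare partial AE dates with the month and year of Amendment 6 consent, and use the consent date as the reference in the AE onset rules. Word the second onset rule as on or after that date, so that a previous visit on the consent date is covered. State in SAP 5.3 that these definitions prevail over the cited rulebook.
3. In SAP 3.2, 5.2.2, 6.2.3.1 and 6.2.3.5, state that first dose means the first non-zero dose after Amendment 6 consent (of the drug concerned, for duration), as Protocol 9.4.1 does for treatment duration.

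The cost is SAP wording and one derived variable. Protocol 1.3 already puts the Amendment 6 consent date and the AEs on the CRF.
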